### **Brief Summary**

[figure not shown]
The study aims to validate naevia medical, a knowledge-based clinical decision support system (CDSS), for clinical benefit and safety in cases of cardiac valvulopathies. Using a series of retrospective clinical cases of heart valve disease, the research will evaluate the number of appropriate and inappropriate recommendations during baseline measurement (conventional management) and after CDSS activation.

Dilemma Solutions S.L.	CHAPTER 06-1C	TD01-06-1C Ver.: 01 2025/03/03
	CLINICAL EVALUATION PLAN (CEP)	Page 1 of 38

Dilemma Solutions S.L.	CHAPTER 06-1C	TD01-06-1C Ver.: 01 2025/03/03
	CLINICAL EVALUATION PLAN (CEP)	Page 4 of 38

## 1. Purpose / Objective of Clinical Evaluation Plan

As required under Article 61 and Annex XIV, Part A (1)(a) of Regulation (EU) 2017/745 (hereafter MDR), this Clinical Evaluation Plan (CEP) is to establish, specify and justify critical aspects related to the device under evaluation (DUE) before proceeding with subsequent steps to locate, appraise and analyse available clinical data and prior to establishing the Clinical Evaluation Report (CER).

In particular this CEP provides the basis and justification for the level of clinical evidence required for the DUE.

[figure not shown]
The level of clinical evidence is determined in view of the characteristics of the device and its intended purpose and is fundamental to enable the acceptability of the benefit-risk ratio to be established.

Methods to enable identification and evaluation of available clinical data relevant to the DUE and its intended use are specified, in order to enable a conclusion to be reached concerning the sufficiency of the available clinical data establishing the safety and performance of the device.

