### Evidence from clinical evaluation/investigations

- Software enables to provide recommendations and suggestions for knowledge related to diagnosis, prognosis and/or treatment: scientific literature confirms that SW system functions and features are aligned with current user requirements as described in relevant publications and as included in the DUE.

Dilemma Solutions S.L.	CHAPTER 06-1C	TD01-06-1C Ver.: 01 2025/03/03
	CLINICAL EVALUATION PLAN (CEP)	Page 13 of 38

- Increase of appropriate recommendations: number of appropriate recommendations – an observational, single-centre study consisting on a clinical validation of a CDSS applied to retrospective clinical cases of cardiology patients with valvular heart disease, shall confirm an increase in the number of appropriate recommendations by by a factor of three over the recommendations generated with general management without the support system.
- Inappropriate recommendations: number of inappropriate recommendations – an observational, single-centre study consisting on a clinical validation of a CDSS applied to retrospective clinical cases of cardiology patients with valvular heart disease, shall confirm that naevia medical, compared to conventional management, is able to reduce the number of inappropriate and mising recommendations based on scientific evidence in the diagnostic and therapeutic areas.
- Concordance between expert evaluators:
  - o The analysis of the degree of agreement/disagreement in the different domains, evaluated using a Likert scale, analysed using ordinal regression (Joshi, Kale et al. 2015). Response options: 1. Strongly disagree, 2. Disagree, 3. Neither agree nor disagree, 4. Agree, 5. Strongly agree.
  - o The panel's agreement with the CDSS was very high, with a mean Likert scale score above 4 in all domains (STD: 4.53, LTD: 4.68, CMT: 4.58, ITI: 4.62). The probability of strongly agreeing was significantly higher than the probability any of the other categories (z.ratio (5|1)= 30.88, p-value< 0.001, z.ratio (5|2)= 31.67, p-value < 0.001, z.ratio (5|3) = 30.21, p-value< 0.001, z.ratio (5|4)= 22.54, p-value< 0.001).

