	43(7), https://doi.org/10.1093/eurheartj/ehab395	561-632.		
Appropriate recommendations	Increase the number of appropriate recommendations by a factor of three	Clinical	-	An observational study consisting on a clinical validation of a CDSS applied to retrospective clinical cases of cardiac patients with valvular heart disease, shall confirm an increase in the number of appropriate recommendations by a factor of three over the recommendations generated with conventional management without the support system.
Inappropriate recommendations	Reduction of inappropriate recommendations	Clinical	-	An observational study consisting on a clinical validation of a CDSS applied to retrospective clinical cases of cardiac patients with valvular heart disease, shall confirm that Naevia medical, compared to conventional management, is able to significantly decreased the number of inappropriate and missing recommendations in all the domains analyzed.

Dilemma Solutions S.L.	CHAPTER 06-1C	TD01-06-1C Ver.: 01 2025/03/03
	CLINICAL EVALUATION PLAN (CEP)	Page 27 of 38

Concordance between expert evaluators	Professionals agreement [reference to sources]  *Joshi, A., S. Kale, S. Chandel and D. K. Pal (2015). "Likert Scale: Explored and Explained." Current Journal of Applied Science and Technology 7: 396-403.	Clinical	
 
- The panel's agreement with the CDSS was very high, with a mean Likert scale score above 4 in all domains (STD: 4.53, LTD: 4.68, CMT: 4.58, ITI: 4.62). The probability of strongly agreeing was significantly higher than the probability any of the other categories (z.ratio (5 1)= 30.88, p-value< 0.001, z.ratio (5 2)= 31.67, p-value < 0.001, z.ratio (5 3) = 30.21, p-value< 0.001, z.ratio (5 4)= 22.54, p-value< 0.001).
 
-
 

Safety of Naevia medical			

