## Overview

This is the first Clinical Evaluation Plan according to the Regulation (EU) 2017/745 on medical devices, since the DUE, NAEVIA MEDICAL, has not been on the market before (2017).

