## Clinical Investigations Undertaken

The following tables summarize the clinical investigations that have been placed for the DUE:

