### Main clinical investigation

Title	Clinical validation study of naevia medical, a decision support tool for valvular heart disease
Registration number	ClinicalTrials.gov ID NCT06392464
Start and End	2024
Publication	Pending
Design	pre-test-post-test of a randomly assigned group, using a longitudinal repeated measures approach and retrospective validation
Duration	3 months
Centres	Instituto de Investigación Sanitaria de Santiago de Compostela (IDIS)
Sponsor	DILEMMA SOLUTIONS SL
Main objective	Demonstrate that the use of the naevia medical CDSS significantly increases appropriate recommendations based on clinical practice guidelines, and decreases the number of inappropriate recommendations received by the patient, compared to conventional management.
Device investigation under	Naevia medical
Number of participants	101

Dilemma Solutions S.L.	CHAPTER 06-1C CLINICAL EVALUATION PLAN (CEP)	TD01-06-1C Ver.: 01 2025/03/03
		Page 33 of 38

Title	Clinical validation study of naevia medical, a decision support tool for valvular heart disease	
Inclusion criteria	
Retrospective clinical retrospective cases of patients with valvular heart disease will be selected in a stratified randomised manner from among:
 
 
(i) patients presented at a medical-surgical session.
 
ii) patients from the monographic consultation of valvopathies.
 
 
Inclusion criteria:
 
 
- Clinical cases of patients randomly selected from among those presented during the year 2022 in medical-surgical session with the main diagnosis of aortic valvular stenosis, aortic insufficiency, mitral stenosis and mitral insufficiency (greater than moderate grade). Randomisation will be stratified ensuring that 50% come from the medical-surgical session.
 
- Clinical cases of patients randomly selected from clinical records of the Valvopathy Consultation seen in 2022 with the main diagnosis of aortic stenosis, aortic insufficiency, mitral stenosis and mitral insufficiency (major degree).
 
mitral regurgitation (greater than moderate grade). Randomisation will be stratified by ensuring that at least 40% of patients have aortic valve disease and 20% have mitral valve disease.
 
- Age <math>\geq 18</math> years.
 
	

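### Table 1 cannot serve as evidence that the main-study acceptance criteria were pre-specified: one entry is an observed result, and another differs from the study's own threshold

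*Protocol*

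**What the plan says.** Section 1 describes the plan as written "before proceeding with subsequent steps to locate, appraise and analyse available clinical data and prior to establishing the Clinical Evaluation Report (CER". The page header throughout, including the pages of Table 1, reads "TD01-06-1C Ver.: 01 2025/03/03", and the Overview in Section 14 states: "This is the first Clinical Evaluation Plan according to the Regulation (EU) 2017/745 on medical devices".

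Section 14 lists the main study under the heading "Clinical Investigations Undertaken", with start and end both given as 2024, a duration of 3 months and 101 participants. The text after Table 1 in Section 11 says that the device's preclinical and clinical studies are available.

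Two rows of Table 1 matter here:

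- **Concordance between expert evaluators.** The acceptance column gives four domain means and then, in the past tense, "The probability of strongly agreeing was significantly higher than the probability any of the other categories", with z-ratios and p-values. Section 7.1 repeats the same text.
- **Appropriate recommendations.** The measure is "Increase the number of appropriate recommendations by a factor of three", and the acceptance column says that the retrospective valvular study is to confirm it.

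The outcomes cell for the main study in Section 14 treats a 15% increase over conventional management as clinically beneficial. It defines the percentage as (post-intervention − baseline) / baseline × 100. The SAP states no threshold. It specifies per-patient counts and a Wilcoxon signed-rank test.

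**The concern.** An acceptance criterion supports a confirmatory claim only if it was fixed before the result was known. A plan that describes itself as preceding the analysis invites the reader to treat everything in Table 1 that way. For the concordance row this cannot be right, because the entry is itself an analysed result. For the factor of three, the plan gives no date or source, and the figure disagrees with the one stated for the study.

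If Table 1 is followed as written, the evaluation report could present the agreement figures as a criterion that was met. It could also judge the appropriate-recommendation count against a mark that contradicts the study's own.

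**Working it through.** The documents give no sample-size, power or alpha calculation on this point, so there is no design figure to reproduce. The check is chronological, with simple arithmetic on the two thresholds.

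**1. Dates.** The plan is dated 3 March 2025; the study started and ended in 2024 and lasted 3 months.

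- Latest possible end, 31 December 2024: the plan follows by 62 days.
- Earliest possible end, 1 January 2024 plus 3 months = 1 April 2024: the plan follows by 336 days.

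The plan postdates the study on either reading. It calls itself the first such plan, so the documents show no predecessor in which the Table 1 criteria could have been fixed.

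**2. The concordance row.** The entries are means of 4.53, 4.68, 4.58 and 4.62, and z-ratios of 30.88, 31.67, 30.21 and 22.54, each with p < 0.001. The smallest z-ratio gives a two-sided normal p of about 1.7 × 10⁻¹¹², which agrees with the printed bound. A test statistic reported to two decimals with its p-value is an output of analysis and cannot be a planned pass mark. The row contains no other criterion.

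**3. Which study the agreement figures come from.** The plan does not attribute them. The SAP has a panel of 3 experts label recommendations as appropriate, inappropriate or missing and, as the last step, grade agreement with the CDSS on five levels. Section 7.1 lists a five-level scale and a panel. None of the other studies listed in Section 14 reports a Likert outcome. The main study is therefore the very probable source, by inference.

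**4. The two thresholds on one scale**, using the Section 14 formula:

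- Factor of three: (3 − 1) / 1 × 100 = +200%.
- Main study's outcomes cell: +15%, a factor of 1.15.
- Ratio of the two: 200 / 15 = 13.3.

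With an assumed baseline of 4 appropriate recommendations per patient (illustrative only), the marks would be 4 × 1.15 = 4.6 and 4 × 3 = 12. Any observed ratio from 1.15 up to, but not including, 3 meets one mark and fails the other. The ratio of 13.3 measures how far the thresholds disagree. It says nothing about when either was set.

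**5. Is there support elsewhere?** The SAP contains neither threshold. The outcomes cell cites a separate study protocol, which is not among the documents. The 15% also reaches the reader only through the 2025 plan, so the documents date neither figure.

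**The case against.** The best reply is that Section 1 refers to the stages of a clinical evaluation applied to data that may already exist. Section 9.2 sets out planning first, then identification, appraisal and analysis, and one of its search strategies expressly covers a device that has already been through a clinical investigation. Section 14 lists the main study openly. This stands: a plan dated after a completed study does not, by its date alone, contradict Section 1. The conflict comes from results already analysed and placed in an acceptance column.

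A reader might also infer that the factor of three was read off the data and is therefore met by construction. The documents do not support that. Neither quotes any count of appropriate, inappropriate or missing recommendations, the publication is given as pending, and the study protocol cited in Section 14 might contain a dated criterion. Because the same panel pass yields both the counts and the agreement grades, the counts had probably been collected when the plan was written. That makes the inference possible, not shown.

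Nor does the point reach all of Table 1, which is titled as an indicative list. The preclinical verification and usability rows, and the safety criteria drawn from literature, vigilance or post-market data, do not depend on this study. The direction of the inappropriate-recommendation criterion agrees with the objective stated for the main study.

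Finally, the SAP's Wilcoxon comparison uses neither threshold, so that test is not affected. What remains open is the acceptance decision in the plan.

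**Conclusion.** The point holds for the criteria that rest on the main study. The concordance entry is a result and not a criterion; this follows directly from the text of Table 1. That it is the main study's result is a strong inference from the panel, the scale and the absence of another candidate study. As printed, it conflicts with Section 1's account of the plan as preceding analysis.

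The factor of three (+200%) differs from the only threshold stated for the study (+15%) and is absent from the SAP. The plan cannot show that it was fixed before the data were seen. Nor do the documents show that it was fixed afterwards: its timing is undocumented. The cited study protocol could settle the question either way.

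**What to change.** 1. In Table 1 and Section 7.1, label the concordance entry as a result already observed, and do not use it as an acceptance criterion.
2. Reconcile 15% with the factor of three. Use for acceptance only the threshold in the dated study protocol, and cite that document. Report any threshold that cannot be shown to predate data access as a labelled post hoc description.
3. For each Table 1 criterion that rests on the main study, state its source and its date relative to data access.
4. Amend Section 1 to say that main-study results were already available when the plan was written.

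The cost is wording in Section 1, Section 7.1 and Table 1. No new data or analysis is needed. The headline claim may become less favourable if the factor of three cannot be traced to a source that predates the data.

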## 2. Scope of the Clinical Evaluation Plan

This Clinical Evaluation Plan is related to the Clinical Evaluation of the following device (family):

### NAEVIA MEDICAL

*Figure 1. NAEVIA MEDICAL picture*

REFERENCE	PRODUCT NAME / SHORT DESCRIPTION	UDI-DI (GTIN14)
NAEVIA MEDICAL	NAEVIA MEDICAL	(01)08437026776015

Dilemma Solutions S.L.	CHAPTER 06-1C	TD01-06-1C Ver.: 01 2025/03/03
	CLINICAL EVALUATION PLAN (CEP)	Page 5 of 38

### 3. Product description

NAEVIA MEDICAL is software whose ultimate purpose is to provide support to physicians in the process of applying medical practice and scientific clinical knowledge. It is based on the clinical decision support systems (CDSS) paradigm.

Naevia Medical does not use artificial intelligence technologies such as machine learning or generative systems. Instead, it is based on an expert system composed of clinical rules made and validated by healthcare professionals, derived from reliable sources of knowledge and subjected to a rigorous peer-review process.

The solution is implemented on a robust .NET-based platform, fully leveraging the capabilities of the Visual Studio IDE to create an integrated, high-productivity development environment. The programming languages used during its development were C#, JavaScript, HTML and CSS, allowing the development of both back-end components and interactive and responsive user interfaces. This architecture promotes modularity and code reusability, facilitating the scalable and maintainable integration of new modules and functionalities. Furthermore, standardized coding practices and design patterns are adopted to enable early error detection through automated testing and static code analysis, ensuring quality and efficiency at every stage of the development lifecycle. Overall, this technical approach not only maximizes development efficiency but also guarantees the software's adaptability and evolution in response to future technological demands.

The system is designed with a strong emphasis on compatibility, ensuring seamless integration with future upgrades, multiple Software of Unknown Provenance (SOUP) components, and various device versions. To achieve this, the architecture follows a modular and loosely coupled approach, allowing individual components to be updated or replaced without impacting overall system functionality. The implementation adheres to industry best practices to facilitate interoperability across different software versions and hardware platforms. Additionally, rigorous version control and continuous integration practices are employed to guarantee stability and reliability as the system evolves. This approach minimizes disruptions, enhances maintainability, and ensures long-term adaptability to technological advancements.

A fundamental aspect to maintain the security of critical areas in applications is to perform a correct validation of input and output data. In naevia's platform, exhaustive validations of input and output data are implemented and must be complemented by the relevant functional or business logic validations:

Validations are always performed on the server side. Client-side validations can also be useful, but are sufficient.

Fully cover data validation using validation schemes or standard mechanisms that ensure data entry by means of: sanitizations, data type, format, lengths, values, whitelists, blacklists, etc.

Ensure that structured data is strongly typed and validated according to a defined scheme, including allowed characters, length and pattern.

Verify that unstructured data is sanitized to impose generic security measures, such as allowed characters and length, and avoid potentially harmful characters.

Dilemma Solutions S.L.	CHAPTER 06-1C	TD01-06-1C Ver.: 01 2025/03/03
	CLINICAL EVALUATION PLAN (CEP)	Page 6 of 38

Ensures that all untrusted input is properly sanitized using a sanitization library. Avoid displaying sensitive information as a result of a validation error for any parameter received. It accepts only the expected data at each application entry point that comes from the user, from the end process of all input fields, forms, URLs, application cookies, etc. Any unexpected data should be rejected

Verify that server-side input validation errors result in rejection of the request.

Ensures that all database queries are protected using parameterized queries to prevent SQL injection. Checks that the application is not susceptible to command injection. Checks that the application does not contain mass parameter assignment vulnerabilities (AKA automatic variable binding). Ensure that all input data is validated, not just HTML form fields, but all input sources such as REST requests, query parameters, HTTP headers, cookies, batch files, RSS feeds, etc., using whitelists, lesser forms of validation such as greylists (which remove known bad strings) or blacklists (which reject bad input).

The product is a Class IIa medical device according to Rule 11 of Annex VIII of the MDR.

It belongs to the following device categories:

GMDN CODE	GMDN TERM	DESCRIPTION
61087	Clinical management support software	An application software program intended to facilitate clinical management decisions by receiving structured patient data from electronic health records and/or manually-entered information (e.g., demographics, diagnostic/laboratory results) and returning clinical care information (e.g., reports, pedigree diagrams, reminders, post-therapy prognosis/risk score, anesthesia/pharmaceutical dosage, and/or links to guidelines) to a healthcare professional responsible for patient care; it is not primarily intended to analyse or manage diagnostic/patient images. Otherwise known as clinical decision support (CDS) software, it may be a locally installed program, web-based, or mobile application.

EMDN CODE	CATEGORY	CATEGORY DESCRIPTION	EMDN CODE DESCRIPTION
V92	V	Various devices	Medical device software - not included in other classes

Dilemma Solutions S.L.	CHAPTER 06-1C	TD01-06-1C Ver.: 01 2025/03/03
	CLINICAL EVALUATION PLAN (CEP)	Page 7 of 38

### **3.1. Special characteristics of the device that may pose safety concerns**

The DUE does not include medicinal, human, or animal components. It does not have any special characteristics that could pose new safety concerns.

### **4. General safety and performance requirements that require support from relevant clinical data**

For the DUE, and following the Annex XIV (Part A, Section 1) of the MDR, the General Safety and Performance Requirements (GSPR) extracted from the Annex I that require support from relevant clinical data are:

*[GSPR #1] Devices shall achieve the performance intended by their manufacturer and shall be designed and manufactured in such a way that, during normal conditions of use, they are suitable for their intended purpose. They shall be safe and effective and shall not compromise the clinical condition or the safety of patients, or the safety and health of users or, where applicable, other persons, provided that any risks which may be associated with their use constitute acceptable risks when weighed against the benefits to the patient and are compatible with a high level of protection of health and safety, taking into account the generally acknowledged state of the art.*

Relevant clinical data are to be located concerning:

- Device clinical performance. Increasing the number of appropriate diagnostic and therapeutic recommendations compared to conventional medical management.
- Device clinical safety. The product aims to provide this support safely for the patient, without generating inappropriate recommendations under normal conditions of use.
- Clinical conditions of the patient population and clinical outcomes following use of the device
- Clinical benefits related to the use of the device. Increasing adherence to scientific recommendations
- Clinical risks related to the use of the device. Generate recommendations and suggestions of knowledge that do not apply to the patient's data.
- Acceptability of the benefit-risk profile → Compatibility with a high level of protection of health and safety

The purpose of the product is to add value to healthcare professionals in the decision-making process by increasing appropriate recommendations based on scientific evidence and decreasing inappropriate recommendations. Its use aims to promote the practice of scientific medicine, with greater adherence to scientific recommendations that have been shown to improve patient outcomes.

Dilemma Solutions S.L.	CHAPTER 06-1C	TD01-06-1C Ver.: 01 2025/03/03
	CLINICAL EVALUATION PLAN (CEP)	Page 8 of 38

It is important to emphasize that naevia medical does NOT replace the physician nor does it make autonomous decisions regarding patient management; its function is limited to presenting a prioritized series of knowledge recommendations that the professional can review and choose to adopt or not. These recommendations are explainable by showing the facts that triggered the recommendation, reproducible, and supported by information referenced in bibliographic citations. In this regard, naevia medical does NOT use artificial intelligence algorithms based on case learning nor does it employ generative technologies.

The product aims to provide this support safely for the patient, without undesirable side effects or adverse events under normal conditions of use.

*[GSPR #2] The requirement in [Annex I of the MDR] to reduce risks as far as possible means the reduction of risks as far as possible without adversely affecting the benefit-risk ratio.*

Relevant clinical data are to be located concerning:

- Acceptability of the benefit-risk profile → Compatibility with a high level of protection of health and safety

The risk-benefit relationship is favourably justified when the benefits in improving the quality of care, increasing appropriate recommendations, and decreasing inappropriate ones outweigh the risks associated with the use of CDSS. This requires careful modelling of knowledge, correct implementation, constant monitoring, and continuous updating. Acceptance of the system by clinical users is crucial and must be ensured through appropriate training, support, and participation in system improvement.

Deterministic rules are widely used for problem-solving. The application of a set of clinical rules to the specific data of a patient enables the logical generation of recommendations and allows for the review of knowledge that applies to a particular case. However, it should be considered that there is intrinsic uncertainty in each decision-making problem, and the medical knowledge managed by a system has limitations.

With the objective of reducing risks the knowledge modelling and rule-making system of naevia medical facilitates semantically well-formed rules with coherent logic. The peer review process aims to ensure that the variables and propositions used have the same meaning as the texts of the recommendations they intend to model.

*[GSPR #4] Risk control measures adopted by manufacturers for the design and manufacture of the devices shall conform to safety principles, taking account of the generally acknowledged*

Dilemma Solutions S.L.	CHAPTER 06-1C	TD01-06-1C Ver.: 01 2025/03/03
	CLINICAL EVALUATION PLAN (CEP)	Page 9 of 38

state of the art. To reduce risks, Manufacturers shall manage risks so that the residual risk associated with each hazard as well as the overall residual risk is judged acceptable. In selecting the most appropriate solutions, manufacturers shall, in the following order of priority: **(a)** eliminate or reduce risks as far as possible through safe design and manufacture; **(b)** where appropriate, take adequate protection measures, including alarms if necessary, in relation to risks that cannot be eliminated; and **(c)** provide information for safety (warnings/precautions/contra-indications) and, where appropriate, training to users. Manufacturers shall inform users of any residual risks.

Relevant clinical data is to be located concerning:

- Generally acknowledged state of the art as related to clinical, biological, and technical aspects of the DUE
- Information for safety / training to users currently provided with similar devices on the market
- Known and foreseeable residual risks currently related to similar devices on the market

[GSPR #5] In eliminating or reducing risks related to use error, the manufacturer shall **(a)** reduce as far as possible the risks related to the ergonomic features of the device and the environment in which the device is intended to be used (designed for patient safety), and **(b)** give consideration to the technical knowledge, experience, education, training and use environment, where applicable, and the medical and physical conditions of intended users (design for lay, professional, disabled or other users).

Relevant clinical data is to be located concerning:

- Specific usability / use-error risks that are known or foreseeable
- Information for safety / training to users currently provided with similar devices on the market

Naevia medical is designed to be used by physicians after a short training period aimed at eliminating any errors in usage. Specific usability/use-error risks that are known or foreseeable should be considered. Safety/training information currently provided to users of similar devices on the market must also be taken into account. The transparency of the software's knowledge recommendations, which simply explain the conditions that triggered them, allows the professional to interact with and critically analyze the suggestions.

[GSPR #6] The characteristics and performance of a device shall not be adversely affected to such a degree that the health or safety of the patient or the user and, where applicable, of other persons are compromised during the lifetime of the device, as indicated by the manufacturer, when the device is subjected to the stresses which can occur during normal conditions of use and has been properly maintained in accordance with the manufacturer's instructions.

Dilemma Solutions S.L.	CHAPTER 06-1C	TD01-06-1C Ver.: 01 2025/03/03
	CLINICAL EVALUATION PLAN (CEP)	Page 10 of 38

Relevant clinical data is to be located concerning:

- Normal conditions of use of the DUE, including other devices interconnected or used together with the DUE
- Information for proper maintenance currently provided with similar devices on the market
- Clinical data to support the clinical safety and performance of the device throughout the claimed lifetime of the device.

The system's knowledge is updated throughout the lifetime of the knowledge version, incorporating the necessary fine-tuning to facilitate updating and the correct interpretation of the recommendations. This includes normal conditions of use and clinical data to support the clinical safety and performance of the device throughout its claimed lifetime.

*[GSPR #8] All known and foreseeable risks, and any undesirable side-effects, shall be minimised and be acceptable when weighed against the evaluated benefits to the patient and/or user arising from the achieved performance of the device during normal conditions of use.*

Relevant clinical data are to be located concerning:

- State of the art concerning known clinical risks and side-effects
- Clinical benefits related to the use of the device
- Clinical risks related to the use of the device
- Acceptability of the benefit-risk profile

Risks and potential adverse effects will be monitored and controlled.

In relation to the potential benefits, Naevia medical provides recommendations to doctors based on the latest evidence and clinical guidelines, supporting informed and updated decision-making. It promotes consistency in care by standardizing data presentation and encouraging evidence-based practice, reducing variability in patient treatment and clinical inertia. Additionally, the CDSS reduces medical errors by offering knowledge-based suggestions, particularly in high-pressure environments with complex patients, and serves as an educational tool, keeping professionals informed about scientific updates while they perform their clinical duties.

*[GSPR #23] Label and instructions for use: (4) Information in the instructions for use (e) the performance characteristics of the device.*

Relevant clinical data are to be located concerning:

- State of the art concerning known clinical risks

Dilemma Solutions S.L.	CHAPTER 06-1C	TD01-06-1C Ver.: 01 2025/03/03
	CLINICAL EVALUATION PLAN (CEP)	Page 11 of 38

Detailed usage instructions on the platform itself, as well as updated information on the latest evidence.

